## **I. LIST OF ABBREVIATIONS**

AR	Adverse Reaction
CI	Chief Investigator
CNORIS	Clinical Negligence and Other Risks Insurance Scheme
CRF	Case Report Form
DMS	Data Management System
GCP	Good Clinical Practice
ICF	Informed Consent Form
ICG	Indocyanine Green
ISF	Investigator Site File
ISRCTN	International Standard Randomised Controlled Trials
MedDRA	Medical Dictionary for Regulatory Authorities
NHS R&D	National Health Service Research & Development
PDE	Photo Dynamic Eye
PI	Principal Investigator
PIS	Participant Information Sheet
REC	Research Ethics Committee
SLN	Sentinel Lymph Node
TASC	Tayside medical Science Centre
TCTU	Tayside Clinical Trials Unit
TMF	Trial Master File
TMG	Trial Management Group
TSC	Trial Steering Committee

## II. TRIAL SUMMARY

Trial Title	A prospective randomised study comparing indocyanine green (ICG) fluorescence combined with a standard tracer versus ICG alone for sentinel lymph node (SLN) detection in early breast cancer	
Internal ref. no. (or short title)	Indocyanine green Node FLUorEsceNCE study: INFLUENCE	
Trial Design	Multicentre, 2-arm, randomised, controlled intervention versus standard care	
Trial Participants	Women diagnosed with invasive breast cancer	
Planned Sample Size	100	
Treatment duration	Single intra-operative intervention	
Follow up duration	Routine post-operative review at 2 weeks and telephone consultation at 3 months	
Planned Trial Period	3 months	
	Objectives	Outcome Measures
Primary	To determine the sensitivity of fluorescence imaging alone for SLN identification compared with a combination of ICG and a standard tracer (blue dye or radioisotope)	Percentage of patients with successful identification of the SLN using ICG alone or combined with a standard tracer, stratified by cohort
Secondary	Procedural node positivity rates	Proportion of SLN biopsy cases with tumour deposits in at least one node (including macrometastases, micrometastases and isolated tumour cells)
	Adverse events from SLN biopsy	Seroma formation Cutaneous staining
Intervention	ICG fluorescence as single tracer	

### **III. FUNDING AND SUPPORT IN KIND**

#### **FUNDER(S)**

Association of Breast Surgery

The NHS Tayside Breast Endowment Fund

### **IV. ROLE OF TRIAL SPONSOR AND FUNDER**

The sponsor assumes overall responsibility for the initiation and management of the trial.

Trial design, conduct, data analysis and interpretation, manuscript writing, and dissemination of results will remain the responsibility of the sponsor. The sponsor will maintain the right for the final decision regarding any of these aspects of the trial. Funding provided does not infer any governance of the research or supervision of the conduct of the research by the funders.

### **V. ROLES AND RESPONSIBILITIES OF TRIAL MANAGEMENT COMMITTEES/GROUPS & INDIVIDUALS**

The trial will be coordinated by a Trial Management Group (TMG), consisting of the grant holders, including the CI, collaborators, statistician, trial manager and research nurse where appropriate. Details of membership of the TMG will be held in the Trial Master File (TMF). The TMG will meet regularly to ensure all practical details of the trial are progressing well and working well and everyone within the trial understands them. Minutes of the TMG meetings will be maintained in the TMF.

The functions of the Trial Steering Committee (TSC) will be undertaken by the TMG. No independent TSC will be convened for this trial.

The functions of the Data Monitoring Committee will be undertaken by the TMG. No independent DMC will be convened for this trial.

The CI will be responsible for the conduct of the trial. Site delegate(s) will oversee the trial and will be accountable to the CI. A trial-specific Delegation Log will be prepared for each Site, detailing the duties of each member of staff working on the trial.

The trial will be conducted in accordance with the principles of GCP.

In addition to Sponsorship approval, a favourable ethical opinion will be obtained from an appropriate NHS REC. Authorisation from appropriate National Health Service Research & Development (NHS R&D) permission(s) will be obtained prior to commencement of the trial.

**VII. KEY WORDS: fluorescence, sentinel lymph node (SLN), breast cancer**

**VIII. TRIAL FLOW CHART**

## 1. BACKGROUND

Fluorescence navigation using the fluorochrome ICG has been employed to visualise lymphatic channels and nodal tissue for identification of SLN(s) in breast and other site cancers. The fluorescent signal is captured by a photodynamic eye composed of a series of light emitting diodes (LEDs) that produce light at a wavelength of 760nm, a lens and a filter. The detector is a charge coupled device camera that filters out wavelengths below 820nm. The fluorescent signals appear on a TV monitor. Fluorescence develops immediately following intra-dermal/subareolar injection of ICG and within seconds can be seen in the subcutaneous vessels of the breast. The illuminated subcutaneous lymphatic channels can be visualised on the Photo Dynamic Eye (PDE) display and progression of the ICG within the lymphatic system tracked as it passes towards the axilla. The fluorescence is scattered by superficial tissues and cannot be detected at a depth of more than 1cm with current technology. The fluorescent signal is lost from scattering and technical improvements are aimed at reducing scatter and improving sensitivity (e.g. development of a PDE which can detect fluorescence at a depth of up to 2cm). Pressure applied to the axillary region enables lymph nodes to be visualised percutaneously before the skin incision is made. The fluorescent lymphatic channels disappear around the level of the lower axilla and can otherwise only be detected (together with sentinel nodes) after the skin incision has been made. This point at which the subcutaneous lymphatic channels cease to be seen is used to determine the site of skin incision. Application of pressure may permit visualisation of a sentinel node through the skin, but otherwise an incision is made at the point where the fluorescent lymphatics disappear.

Early validation studies used ICG alone with reports of identification rates in excess of 90%. Subsequent practice has favoured a combination of ICG with either blue dye or radioisotope that allows both conventional and fluorescent visualisation of the lymphatic vessels and nodes. These have all shown high levels of nodal recognition by fluorescence with few nodes (<5%) being classified as blue and/or hot but not fluorescent. The ICG-10 study confirmed that combined nodal sensitivity is higher for blue dye and ICG (95.0%) compared with the standard combination of blue dye and radioisotope (73.1%).

Recent studies have shown high levels of concordance (>90%) for SLN detection not only between ICG and blue dye but also ICG and radioisotope. Fluorescence imaging provides at least equivalent detection rates but offers an additional dimension to the technique of SLN biopsy and is safe with in frequent allergic reactions. The combination of ICG with a standard tracer agent represents a transition phase and we now wish to explore ICG as a sole tracer having accrued clinical experience with its usage. In a comparison of ICG as a sole tracer versus radioisotope performed in Japan identification rates for ICG alone and radiocolloid were 98.7% and 96.7% respectively. ICG combines many of the advantages of blue dye and radioisotope without the disadvantages. Tracer combinations with dual localisation are more expensive and inconvenient than ICG alone but not necessarily associated with improved accuracy that is significant in terms of clinical outcomes.

## 2. RATIONALE

More than half of newly diagnosed breast cancer patients will undergo routine SLN biopsy annually in the UK (>25,000 cases). Blue dye is becoming less popular as a tracer due to potential allergic reactions and staining of cutaneous/breast tissues. Drawbacks of radioisotope include availability, cost, patient inconvenience/discomfort, radiation exposure/disposal and mandatory licensing. Fluorescence navigation has high optical sensitivity and permits a real-time sequential SLN dissection guided by visualisation of lymphatic tissue and sentinel nodes that is not possible with radioisotope alone. In particular, identifying sentinel nodes in order of 'biological' priority is more difficult with radioisotope whereby nodes are

detected as hotspots irrespective of anatomical lymphatic flow. The fluorescent node(s) acts as a 'beacon' that can aid dissection within a fatty axilla (patients with high body mass index). Hence there are potential drawbacks from use of both blue dye and radioisotopes for SLN localisation in breast cancer. Moreover, radioisotopes are a by-product of a contracting nuclear industry and supply might become unpredictable with widespread usage in the emerging economies of India, China and Brazil. This may lead to increased costs and render alternative tracer agents more attractive in terms of surgical technique, safety and patient convenience/comfort but also cost-effectiveness. The proposed study could be a forerunner to a larger multicentre trial evaluating ICG alone. Localisation techniques using a non-radioactive tracer with a real-time visual component warrant further investigation to confirm equivalence in performance compared to standard tracer agents.

ICG is a less expensive tracer than radioisotope although initial capital equipment costs (PDE camera) are higher. Nonetheless, in the longer-term use of ICG is likely to be more cost-effective than radioisotope taking account cost of the radioisotope injection per patient. Moreover, in a COVID-19 environment, additional visits to the nuclear medicine department can be avoided with use of ICG, whether this is on the day of surgery or before. The eventual use of ICG in place of radioisotope has the potential benefits of avoiding radioactive materials and problems of waste disposal and monitoring. Dispensing with the requirements for radioisotope facilities and mandatory licensing could save the NHS between £100 and £200 per patient. It is also important to stress that this is just for the cost of the radiocolloid injection. In addition to potential cost savings from avoiding necessity of a nuclear medicine facility, there are logistical advantages relating to booking and organising appointments for radiocolloid injection whether this be the day before or same day as surgery.

It is hypothesized that fluorescence mapping can provide at least equivalent sentinel detection rates but offer the opportunity for avoiding blue dye and eventually lead to improved cost-effectiveness if radioisotope is eventually abandoned for routine SLN biopsy. Abolition of blue dye with its associated risk of anaphylactic reaction (1-3%), skin tattooing and non-licensed use will be notable benefits of ICG. Of note, in a UK-Turkish study blue discoloration persisted at the injection site after 12, 24, and > 36 months in 36.5, 23.6, and 8.6% of the patients respectively.

## **2.1. Assessment and Management of Risk**

Standard SLN detection techniques involve the use of blue dye or radioisotopes. ICG fluorescence detection is an alternative tracer agent that has been used in combination with these standard techniques. Participants in this study will be divided amongst two cohorts. Participants in Cohort 1 will be randomised to either ICG alone (intervention) or ICG plus radioisotope (standard care). Participants in Cohort 2 will be randomised to ICG alone (intervention) or ICG plus blue dye (standard care). There is no evidence that any participants randomised to intervention are at no higher risk than those on standard care.

This trial is categorised as:

Type A = No higher than the risk of standard medical care

See Appendix 1

## **3. OBJECTIVES AND OUTCOME MEASURES/ENDPOINTS**

Hypothesis

ICG as a sole fluorescence tracer provides equivalent detection rates when compared to standard detection techniques using blue dye or radioisotopes in combination with ICG.

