### 3.6. Table of endpoints/outcomes

Objectives	Outcome Measures	Timepoint(s) of evaluation of this outcome measure (if applicable)
Primary Objective To determine the sensitivity of fluorescence imaging alone for SLN identification compared with a combination of ICG and a standard tracer (blue dye or radioisotope)	Percentage of patients with successful identification of the SLN using ICG alone or combined with a standard tracer, stratified by cohort	At the time of SLN biopsy
Secondary Objectives Procedural node positivity rates	Proportion of SLN biopsy cases with tumour deposits in at least one node (including macrometastases, micrometastases and isolated tumour cells)	Post-surgery, when histopathology results are available
Adverse events from SLN biopsy	Seroma formation Cutaneous staining Other adverse reactions to tracers	2 weeks and 3 months

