## **7.10. Withdrawal criteria**

Participants are free to withdraw at any time and are not obliged to give reason(s). The CI, PI or delegate will make a reasonable effort to ascertain the reason(s), both for those who express their right to withdraw and for those lost to follow up, while fully respecting the individual's rights.

The investigator may withdraw a patient at any time if it is in the best interest of the patient and treatment continuation would be detrimental to the patients' wellbeing. A full explanation will be provided. If the trial is being conducted on an intention to treat basis, and the participant has been randomised and given the intervention or standard care, they will be asked to complete trial visits as per the protocol, if the CI considers it appropriate, to allow for an intention to treat analysis - but will be censored in the per-protocol analysis. Participants are free to refuse to do so.

Those withdrawn, including those lost to follow-up, will be identified and a descriptive analysis of them provided, including the reasons for their loss, if known, and its relationship to treatment and outcome.

If a participant withdraws or is withdrawn, they will also have the right to withdraw their data and any research tissue collected. Data collected up to the point of withdrawal will be retained and used for analysis unless a participant expresses their right to withdraw their data.

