#### 9.2.1. Summary of baseline data and flow of patients

**No adjustment for baseline characteristics will be required**

#### 9.2.2. Primary outcome analysis

The primary analysis will be performed on the Intention to treat population, for each cohort (Cambridge/ Dundee) separately. As this is not a hypothesis generating trial, all analysis will be exploratory.

Within each group, the number of SLNs for each patient will be recorded numerically in the following categories:

	Study Arm	
Number of SLNs	ICG plus radioisotope or blue dye (standard care)	ICG alone (intervention)
Fluorescence only		
Radioisotope plus fluorescence		
Radioisotope only		
Blue dye plus fluorescence		
Blue dye only		

Pathological exam metastases		
------------------------------	--	--

The proportion of patients within each designated category will be recorded and nodes found on pathological examination to contain metastases documented. Comparison is performed on a procedural basis (proportion of patients with a positive node) using logistic regression with patient positive yes/no.

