### **9.4. Participant population**

The Intention to Treat population will consist of all participants who underwent surgery. All analysis will be based on this population.

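### The hypothesis is equivalent detection rates, but section 9.2.2 has no between-arm comparison of SLN identification: its one comparison is a logistic regression on node positivity

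*Protocol*

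**What the plan says.** **Hypothesis.** Section 3 states that "ICG as a sole fluorescence tracer provides equivalent detection rates when compared to standard detection techniques" (blue dye or radioisotope, each combined with ICG). Section 2 puts it as at least equivalent: "It is hypothesized that fluorescence mapping can provide at least equivalent sentinel detection rates".

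**Primary outcome.** The table in section 3.6 gives "Percentage of patients with successful identification of the SLN using ICG alone or combined with a standard tracer, stratified by cohort". Node positivity per procedure is a secondary outcome in the same table.

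**Primary analysis.** Section 9.2.2 sets out a table of detection categories by arm and says proportions of patients in each will be recorded. It then states: "Comparison is performed on a procedural basis (proportion of patients with a positive node) using logistic regression with patient positive yes/no". Analysis is by cohort, and section 4 gives 25 patients per arm in each cohort. The section also says: "As this is not a hypothesis generating trial, all analysis will be exploratory".

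**Other comparisons.** Section 9.2.3 adds a node-level logistic regression on node positivity, with patient as a random factor, and a comparison of adverse reaction rates. Neither concerns identification.

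**Analysis sets.** Section 9.4 defines the intention-to-treat set as all who had surgery and adds: "All analysis will be based on this population". Section 7.10, in a conditional sentence about withdrawn participants, says they "will be censored in the per-protocol analysis".

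**Sample size.** Section 9.1 bases the 100 on annual case volume. No margin, significance level or power is stated.

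**The concern.** Three parts of the protocol should line up and do not. The hypothesis concerns detection rates, the primary outcome is detection per patient, and the comparison under the primary heading concerns metastasis in the removed nodes. A patient whose sentinel node was found and was tumour-free is a success on the primary outcome and a no in the regression.

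The hypothesis also claims equivalence. That needs an interval for the difference in identification rates, set against a margin. The protocol names neither.

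Two things are at stake. First, the pilot is meant to inform the clinically important difference and the size of a larger trial (section 9.1), and for that it must deliver a usable estimate of the difference in identification with its uncertainty. Second, with so few patients a sizeable loss of detection could be compatible with no statistically significant difference. Failed detection has consequences for patients: Appendix 1 says that axillary nodes are then sampled at random, with a small chance of more seroma and possible lymphoedema.

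**Working it through.** **1. The plan's own figure.** The protocol has no power calculation to reproduce. The count agrees: 2 cohorts × 2 arms × 25 = 100.

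**2. Which outcome is compared.**

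| Item | Section | Outcome |
|---|---|---|
| Hypothesis | 3 | detection rate |
| Primary outcome | 3.6 | SLN identified, per patient |
| Table in the primary analysis | 9.2.2 | detection categories, recorded only |
| Comparison in the primary analysis | 9.2.2 | patient has a positive node |
| Secondary comparisons | 9.2.3 | node positive; adverse reactions |

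No row compares identification between arms.

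**3. What 25 per arm can say about identification.** The Newcombe 95% interval for d = p1 − p2 is built from the Wilson limits (l, u) of each arm:

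- lower = d − √[(p1 − l1)² + (u2 − p2)²]
- upper = d + √[(u1 − p1)² + (p2 − l2)²]

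The Wilson limits are 0.867 to 1.000 for 25/25 and 0.700 to 0.958 for 22/25.

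- *25/25 v 25/25:* d = 0; half-width = 1 − 0.867 = 0.133. Interval: -13.3 to +13.3 points.
- *22/25 v 25/25:* d = -0.12. Lower = -0.12 − (0.880 − 0.700) = -0.30. Upper = -0.12 + √[(0.958 − 0.880)² + (1 − 0.867)²] = -0.12 + 0.154 = +0.034. Interval: -30 to +3 points.
- *Fisher's exact test for 22/25 v 25/25:* 2 × C(25,3)/C(50,3) = 2 × 2300/19600 = 0.235.

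So an observed deficit of 12 points is not significant, and its interval still includes a 30-point loss. The protocol does not name Fisher's test; it is used here only to show the scale.

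**4. Why the logistic regression should not simply be moved to identification.** If one arm has no failures, the maximum-likelihood odds ratio is not finite. Ignoring the negligible chance that an arm has no successes, the probability in one cohort is 1 − (1 − p1²⁵)(1 − p2²⁵).

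| True identification rates | p1²⁵, p2²⁵ | No finite odds ratio |
|---|---|---|
| 98.7% and 96.7% (study cited in section 1) | 0.721, 0.432 | 84% |
| 95% in both (assumed) | 0.277, 0.277 | 48% |
| 90% in both (assumed) | 0.072, 0.072 | 14% |

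**5. The same check on the regression as written.** Section 9.3 expects 7 to 10 node-positive patients in 50, that is 14% to 20%. The chance that an arm of 25 has no positives is 0.86²⁵ = 0.0230 or 0.80²⁵ = 0.0038. Per cohort, 1 − (1 − 0.0230)² = 4.6% and 1 − (1 − 0.0038)² = 0.8%. The planned regression is therefore usually estimable. Its fault is that it models the wrong outcome for the primary analysis.

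**The case against.** The best defence is that this is a pilot. Section 9.1 says it is to inform a larger trial, section 9.2.2 calls all analysis exploratory, and section 9.3 says it is not powered. No significance level or success rule is stated, and nothing says that a non-significant result will be reported as equivalence. Section 9.2 defers to an analysis plan that is not shown, and the choice of interval method normally belongs there. All of this stands, and it lowers the severity. It does not remove the mismatch, because the protocol itself fixes the hypothesis, the primary outcome and a comparison on a different outcome.

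Four stronger readings are tempting and are not supported.

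- *That the primary analysis will often return no estimate.* This is true only of a regression on identification, which the protocol does not specify. For the stated outcome the figure is about 1% to 5% per cohort.
- *That logistic regression as such cannot address equivalence.* It yields an interval that could be set against a margin. What is missing is the right outcome, a margin and precision.
- *That this is the only planned comparison.* Section 9.2.3 has two more, though neither concerns identification.
- *That analysing only the intention-to-treat set biases the trial towards equivalence.* The per-protocol mention in section 7.10 is conditional and concerns withdrawals. The primary outcome is measured at one operation, and no route of crossover to a second tracer is described. This is a wording inconsistency.

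The 98.7% and 96.7% come from one comparison of ICG alone with radioisotope alone, which is not an arm here. Section 1 also reports early ICG-alone rates only as above 90%, which is why the range down to 90% is shown.

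**Conclusion.** The point holds. The protocol hypothesises equivalent detection rates and makes SLN identification primary, but plans no between-arm comparison of it. The comparison in its place concerns a secondary outcome, and no margin or interval rule is stated, so the plan as written cannot support its hypothesis.

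The intervals in steps 3 rest on the planned 25 per arm and separate analysis of each cohort. The best possible result, no failure in either arm, would leave a difference of about 13 points in either direction open. The non-finite-estimate figures of 14% to 84% also depend on assumed or cited true rates, and they count only against one possible repair, not against the plan as it stands.

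Severity is moderate, given the declared pilot and exploratory status.

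**What to change.** - **Section 9.2.2:** make patient-level SLN identification the primary comparison. Report, by arm and cohort, the proportion identified with an exact (Clopper-Pearson) 95% interval. For each cohort, report the risk difference with a Newcombe or Miettinen-Nurminen 95% interval. Do not carry the logistic regression over to this outcome.
- **Section 9.2.3:** move the patient-level node-positivity regression here, in line with its secondary status in section 3.6.
- **Section 3:** reword the hypothesis as estimation of identification rates and their difference, to inform the margin and size of the larger trial. State that a non-significant difference will not be reported as equivalence. Align the matching sentence in section 2.
- **Sections 7.10 and 9.4 (minor):** reconcile them, either by removing the per-protocol wording or by defining such an analysis as supportive.

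The cost is protocol and analysis-plan wording and one table, with no extra patients. The downside is a more modest published claim.
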